After the three core-treatment cycles, up to two additional cycles of ^{177}Lu -OPS201 can be administered if the subject continues to meet the criteria outlined in [Section 6.4.2](#) and the subject has clinical benefit (defined as CR, PR or SD). The additional cycles are optional and must be discussed with the sponsor before administration.

The population of Cohorts 3 and 6 will enrol eight to 10 subjects to ensure a minimum of eight completed subjects. All remaining Cohorts (1, 2, 4, 5, 7 and 8) will enrol three to five subjects to ensure a minimum of three completed subjects per cohort. A completed subject is defined as one who has received at least 3 cycles of study treatment or fewer than 3 cycles if one of the following has occurred: exceedance of organ dose limits, treatment-related safety issues or disease progression.

Figure 2 Study Design - Part B

DRB=data review board; GBq=gigaBecquerel; SRC=safety review committee.

Priority for the conduct of the cohorts is as follows: Cohorts 1 and 3, Cohort 6, Cohort 4, Cohort 5. Each cohort consists of three cycles of treatment. Cohort 2 will not be conducted if 700 μ g or 1300 μ g peptide mass is shown to be optimal. Cohorts 7 and 8 will not be conducted if 1300 μ g peptide mass is seen to be too high. Cohorts 3 and 6 require 10 subjects for eight to be completed. All other cohorts are three to five subjects (minimum of three subjects to be completed).

Radioactivity evaluation (Part A)

In Part A, a cumulative radioactivity of 13.5 GBq (4.5 GBq/cycle \times three cycles) with a peptide mass dose of 300 μ g will be evaluated (Table 2).

In Part B, the radioactivity and peptide mass dosing for each cycle in each cohort is illustrated in Table 2.

Radioactivity escalation (Cohorts 1 and 2 – Part B)

Cohort 1 will investigate a radioactivity of 6 GBq/cycle (cumulative radioactivity 18 GBq) with the same peptide mass dose as in Part A (300 μ g) for three cycles (Table 2).

Once the third subject of Cohort 1 has completed at least two cycles, if no safety signal is observed and if the subjects did not reach the cumulative absorbed dose in each of the target

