organs, Cohort 2 (300 µg; 7.4 GBq/cycle; cumulative 22.2 GBq; [Table 2](#)) will be initiated (see priority classification in [Figure 2](#)). However, if improved safety regarding DLTs is seen with increased peptide mass, Cohort 2 (300 µg; 7.4 GBq/cycle; cumulative 22.2 GBq) may be delayed until experience is gained with the 7.4 GBq dose at the higher peptide mass (700 µg). If optimal peptide mass is evaluated to be >300 µg then this cohort will not be opened.

Intra-individual peptide mass dose evaluation (Cohorts 3 and 6 – Part B)

Cohorts 3 and 6 will allow the intra-individual evaluation of peptide mass. In both Cohorts 3 and 6, subjects will receive the same cumulative radioactivity as in Part A (4.5 GBq/cycle; cumulative, 13.5 GBq; [Table 2](#)). The associated peptide mass dose will also be the same (300 µg) in Cycles 1 and 3, and will be increased to 700 µg in Cohort 3 and 1300 µg in Cohort 6 during Cycle 2.

Peptide mass dose escalation (Cohorts 4 and 5 and optional Cohorts 7 and 8 – Part B)

In Cohort 4, subjects will receive 6 GBq/cycle (cumulative 18 GBq) with a peptide mass dose of 700 µg, for three cycles ([Table 2](#)). After one cycle, if no safety signal is observed in Cohort 4, Cohort 5 will be initiated. In Cohort 5, subjects will receive 7.4 GBq/cycle (cumulative, 22.2 GBq) with a peptide mass dose of 700 µg, for three cycles ([Table 2](#)).

Cohorts 7 and 8 will be cancelled if ssr2 saturation is seen with peptide mass dose of 700µg and 1300 µg in Cohort 3 or 6 and/or if there are other safety signals ([Table 2](#)). There will be no further dose escalation of OPS201 peptide after 1300 µg.

The dose escalation rules

The DRB will consist of a team of “permanent” decision makers (the core team), including selected principal investigators and Ipsen personnel. All final decisions will be made by the core team. The number of DRB meetings may change as needed and the DRB can be called upon rapidly if there is a safety issue of concern in a cohort. The aim is to have all meetings via conference call, but if the timing does not allow for this, then the meeting can be conducted via email exchange or two conference calls with split attendees. A DRB charter will be developed with further details. Ad-hoc DRBs can be convened at any time during the trial.

Dose escalation (peptide mass dose and radioactivity, see [Figure 2](#)) will primarily be decided based on the clinical and safety data of the subjects.

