DLT definition in Part B: IRPP related AEs with a severity of Grade 3 or higher are considered DLTs, with the exception of hair loss, lymphopenia, nonfebrile neutropenia lasting <4 weeks and thrombocytopenia lasting <4 weeks.

Proceeding to the next cohort will be determined by the following DLT rules based on three evaluable subjects:

- if DLTs occur in >33% of subjects in the cohort, the next cohort will not be initiated.
- if DLTs occur in ≤33% and ≥2 of the three subjects have a cumulative absorbed dose in each target organ exceeding the acceptability limits (1.5 Gy in bone marrow (BM) and 23 Gy in kidney), subjects in the next cohort will receive the same cumulative radioactivity or less than in the preceding cohort.
- if DLTs occur in ≤33%, and <2 of the three subjects did not reach the cumulative absorbed dose in each target organ (1.5 Gy in BM and 23 Gy in kidney), the next cohort will be initiated as planned.

Each dose escalation (both peptide and radioactivity) will be carefully evaluated by the DRB. As safety and dosimetry information becomes available in other cohorts, this data will be used to evaluate the on-going cohorts and the subjects’ dosing within the cohorts.

The DRB can make a recommendation as to the radioactivity dosing for the next cohort. This could include continuing the current cohort to complete five subjects for review. Based on the overall safety results, the DRB can also decide to start earlier or delay cohorts depending on the information available. Notification will be given to the principal investigators if this is to occur, with the rationale, as well as to the institutional review board (IRB)/ethics committee (EC).

Number of subjects planned:

Up to 55 subjects with histologically confirmed diagnosis of GEP NETs, lung NETs or pheochromocytoma or paraganglioma will be recruited in the trial:

- Part A: a minimum of six subjects and up to 15 subjects.
- Part B: a minimum of 25 subjects and up to 40 subjects.

For Part B dose escalation, it is anticipated that approximately 40 subjects will be included, in up to eight escalation steps (cohorts). Three to five subjects will be treated per cohort in order to yield a minimum of three completed subjects for three cycles of treatment. For Cohorts 3 and 6, eight to 10 subjects will be treated per cohort to yield a minimum of eight completed subjects. Any cohort can be closed for safety issues before all the subjects are completed.

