The DRB will consist of a team of “permanent” decision makers (the core team), including selected principal investigators and Ipsen personnel. All final decisions will be made by the core team. The number of DRB meetings may change as needed and the DRB can be called upon rapidly if there is a safety issue of concern in a cohort. The aim is to have all meetings via conference call, but if the timing does not allow for this, then the meeting can be conducted via email exchange or two conference calls with split attendees. A DRB charter will be developed with further details. Ad hoc DRBs can be convened at any time during the trial. See [Appendix 3](#) for the details of the review required by the DRB.

Dose escalation (peptide mass dose and radioactivity, see [Figure 13](#)) will primarily be decided based on the clinical and safety data of the subjects.

Dose limiting toxicity (DLT) definition in Part B: IRPP related AEs with a severity of Grade 3 or higher are considered DLTs, with the exception of hair loss, lymphopenia, nonfebrile neutropenia lasting <4 weeks and thrombocytopenia lasting <4 weeks.

Proceeding to the next cohort will be determined by the following DLT rules based on three evaluable subjects:

If DLTs occur in $> 33\%$ of subjects in the cohort, the next cohort will not be initiated.

- If DLTs occur in $\leq 33\%$ and ≥ 2 of the three subjects have a cumulative absorbed dose in each target organ exceeding the acceptability limits (1.5 Gy in BM and 23 Gy in kidney), subjects in the next cohort will receive the same cumulative radioactivity or less than in the preceding cohort.
- If DLTs occur in $\leq 33\%$, and < 2 of the three subjects did not reach the cumulative absorbed dose in each target organ (1.5 Gy in BM and 23 Gy in kidney), the next cohort will be initiated as planned.

Each dose escalation (both peptide mass and radioactivity) will be carefully evaluated by the DRB. As safety and dosimetry information becomes available in other cohorts, this data will be used to evaluate the on-going cohorts and the subjects’ dosing within the cohorts.

The DRB can make a recommendation as to the radioactivity dosing for the next cohort. This could include continuing the current cohort to complete five subjects for review. Alternatively, if any cohort dose (peptide or radioactivity) is closed down, with agreement from the DRB, the

next lowest dose may have three more subjects entered to confirm this is the maximum tolerated dose.

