11.6 Interim Analyses/Safety Review Committees/Data Review Boards

Dosimetry evaluation will be performed on an ongoing basis. After the first six subjects included have completed the study Part A (EOCT/EW Visit) an SRC meeting will be held before exposing the remaining subjects to the entire number of planned administrations. Safety data obtained until 8 weeks after the last administration of the 6th subject will be evaluated during this SRC. Prior to Part B, the SRC will review the safety and dosimetry data of the first six subjects included in Part A.

For Part B, a DRB meeting will be held to review the safety and radiation exposure data and decide whether to proceed with the enrolment of the next cohort dose level and the cumulative radioactivity within a cohort. Each dose escalation (both peptide and radioactivity) will be carefully evaluated by a DRB (see [Figure 13](#) and [Appendix 3](#)).

In addition, the SRC/DRB can be convened at any time during the trial to discuss potential safety issues. The data set to be reviewed by the SRC/DRB is specified in a specific charter.

A first interim analysis will be conducted at the cut-off date of 27 September 2019 to inform the design of the chemotherapy combination study which has been added to the investigational plan.

A second interim analysis of Part B data will be conducted at the EOCT/EOAC/EW (whichever occurs last) after completion of Cohorts 3 and 6. This will provide confirmation of the peptide dose to allow future studies to be developed. It will also confirm if Cohorts 2 or 7 and 8 will be initiated.

A third interim analysis, including all dosimetry, safety and efficacy data, will be performed after the EOCT/EOAC/EW (whichever occurs last) when the two study parts are completed.

The interim analyses may be combined based on the overall study status and subject accrual.

The final analysis will be performed at the end of the 2-year long-term follow-up period.

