DRB-B	Cohort 3 First three subjects, EOC-2	Start Cohort 4 with 6 GBq?	If >65% DLTs in Cohort 3 then NO to Cohort 4. If >33% and <67% DLTs in Cohort 3 Cycle 2 then wait for three more subjects in Cohort 3 Cycle 2 and re-evaluate. Otherwise start Cohort 4. Cohort 4 will not start recruiting until Cohorts 1, 3 and 6 are fully recruited
DRB-C	Cohort 4 EOC-1	Start Cohort 5? Continue Cohort 4?	If >33% DLTs in Cohort 4 then NO to Cohort 5. If >33% DLTs in Cohort 4 then STOP. Evaluate peptide mass dosing and lesion receptor saturation. Evaluate next cohort to start and activity dosing.
DRB-D	Cohort 6 EOC-3 All subjects Cohort 4 EOC-1	Start Cohort 7?	If >33% DLT in Cohort 6 Cycle 2 NO to Cohort 7 AND If lesion receptor saturation in Cohort 6 Cycle 2, then no to Cohort 7 AND If >33% DLTs and <67% DLTs in Cohort 4 and receptor modelling suggests Cohort 7 mass dose safer, then start Cohort 7, otherwise no.
DRB-E	Cohort 6 EOC-3 All subjects Cohort 5 EOC-1	Start Cohort 8?	If >33% DLT in Cohort 6 Cycle 2 NO to Cohort 8 AND If lesion receptor saturation in Cohort 6 Cycle 2, then no to Cohort 8 AND If >33% DLTs <67% DLTs in Cohort 5 and receptor modelling suggests Cohort 8 mass dose safer, then start Cohort 8, otherwise no.
DRB-F	Cohort 1 EOC-3 and Cohort 3 EOC-3 and Cohort 5 EOC-1	Start Cohort 2?	If mass dose modelling suggest 300 ug is optimal AND If >33% DLTs in Cohort 1, AND If >33% DLTs in Cohort 5 Start Cohort 2

DLT=dose limiting toxicity; DRB=data review board; EOC=end of cycle; GBq=gigabecquerel.

Note: At each DRB, safety data available from all cohorts will be evaluated to inform decision making.

a although the DRBs are written in alphabetical sequence this is not a chronological order; each one will be conducted when data becomes available which is dependent on subject recruitment. An ad-hoc DRB can be called to ensure continuity of dosing. Although three completed subjects are required for each completed cycle for evaluation, all available subject data in that cohort will be used (e.g. If five subjects are enrolled and all five complete the end of a cycle prior to the DRB, then all five sets of data will be evaluated).

This cumulative activity in the cohort being evaluated will be determined by the following DLT rules:

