- If, in the preceding cohort after the third administration of ¹⁷⁷Lu-OPS201, DLTs occur in >33% of three subjects (i.e. >1 out of the three to five subjects), the activity for the next cohort will be reduced to a cumulative administered activity which did not lead to DLT occurrence with this frequency.
- If, in the preceding cohort after the third administration of 6GBq ¹⁷⁷Lu-OPS201, DLTs occur in ≤33% of three subjects and ≥2 of the three subjects have a cumulative absorbed

dose in each target organ exceeding the acceptability limits (1.5 Gy in BM and 23 Gy in kidney), subjects in the next cohort will receive the same cumulative activity or less than in the preceding cohort.

- If, in the preceding cohort after the third administration of 6GBq ¹⁷⁷Lu-OPS201, DLTs occur in ≤33% of the three subjects and less than two of the three subjects did not reach the cumulative absorbed dose in each target organ (1.5 Gy in BM and 23 Gy in kidney), the activity in the next cohort will be escalated up to 7.4 GBq per administration, as detailed in the table above

Data Review Board

- the DRB will consist of a team of “permanent” decision makers (the core team);
- principal investigators may participate, present and listen in;
- all final decisions will be made by the core team;
- the number of DRB meetings may change as needed and can be called upon rapidly if there is a safety issue of concern in a cohort;
- the aim is to have all meetings via conference call, but if the timing does not allow for this, then it can be conducted via email exchange or two conference calls with split attendees;
- a DRB charter will be developed with further details.

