5 CHANGES FROM PROTOCOL

Dosimetry sections:

Cumulative absorbed dose to the lesions (Gy) has been added as dosimetry endpoint.

AE section:

AESI definition was updated to “any TEAE related to ¹⁷⁷Lu-OPS201 which occurs the day of ¹⁷⁷Lu-OPS201 administration (same date as ¹⁷⁷Lu-OPS201 administration and at any cycle). “

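### The synopsis lets optional Cohort 2 open after two Cohort 1 cycles, when the whole-course marrow limit tells the board little and before Protocol 11.6 and SAP DRB-F make the same decision

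*Protocol*

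**What the plan says.** The Synopsis, under radioactivity escalation for Cohorts 1 and 2, opens Cohort 2 once the third Cohort 1 subject "has completed at least two cycles, if no safety signal is observed and if the subjects did not reach the cumulative absorbed dose" (the limit set for every target organ). The limits are given under the dose escalation rules and again in Protocol 3.8: 1.5 Gy for marrow and 23 Gy for kidney, both cumulative. The two-cycle trigger appears only in the Synopsis.

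The same decision is timed differently elsewhere:

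- Protocol 11.6, repeated in SAP 3.2.17, places a second interim analysis after Cohorts 3 and 6 are complete and says of it: "It will also confirm if Cohorts 2 or 7 and 8 will be initiated".
- SAP 3.2.19, Table 9, row DRB-F (the row on starting Cohort 2) lists its data as "Cohort 1 EOC-3 and Cohort 3 EOC-3 and Cohort 5 EOC-1", where EOC means end of cycle.
- The activity rules below that table look back "in the preceding cohort after the third administration of 6GBq". They set the next cohort's activity and do not specifically time the opening of Cohort 2.

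Other text limits or qualifies the step. Under Protocol 3.8, if DLTs are at or below 33% but at least two of three subjects exceed the organ limits, "subjects in the next cohort will receive the same cumulative radioactivity or less than in the preceding cohort". The Synopsis adds "The DRB can make a recommendation as to the radioactivity dosing for the next cohort", and that Cohort 2 "may be delayed until experience is gained with the 7.4 GBq dose at the higher peptide mass". Cohort 2 is marked optional and is absent from the stated cohort priority order.

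**The concern.** A cumulative limit tested part-way through a course says little unless the dose is projected to the end of the course, or the limit is scaled down. Here the test is made on a 6 GBq cohort at two cycles and used to open a 7.4 GBq cohort planned for three. A subject can be well inside 1.5 Gy at 12 GBq with a marrow coefficient that would take a Cohort 2 subject past it at 22.2 GBq.

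Two things are at stake. The board could open a cohort whose planned activity cannot be delivered within the protocol's own limits. The team also has conflicting instructions on when to decide. The Synopsis drops Cohort 2 if a higher peptide mass proves optimal, but Cohort 6, which supplies part of that evidence, comes after Cohorts 1 and 3 in priority and may not have reported at the two-cycle point.

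**Working it through.** **Reproducing the plan's activities.** Protocol Table 2: 3 × 6.0 = 18.0 GBq (Cohort 1) and 3 × 7.4 = 22.2 GBq (Cohort 2), as stated. Two Cohort 1 cycles: 2 × 6.0 = 12 GBq, or 13.2 GBq at the +10% tolerance. Protocol 1.7 itself projects linearly: for the ovaries, 0.1 × 22.2 = 2.22, stated as about 2.2 Gy.

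**Marrow coefficients in the protocol.**

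- Section 1.4, investigator study: mean 0.077 Gy/GBq, range 0.049 to 0.11.
- Section 1.6, pilot: mean 0.1 Gy/GBq; one case of 1.3 Gy at 13.7 GBq, so 1.3 / 13.7 = 0.095.

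**Coefficient needed to reach 1.5 Gy** (1.5 / activity):

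- 12 GBq: 0.125
- 13.2 GBq: 0.114
- 18 GBq: 0.083
- 22.2 GBq: 0.068

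**Marrow dose in Gy** (coefficient × nominal activity):

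| Gy/GBq | 12 GBq | 18 GBq | 22.2 GBq |
|---|---|---|---|
| 0.049 | 0.59 | 0.88 | 1.09 |
| 0.077 | 0.92 | 1.39 | 1.71 |
| 0.095 | 1.14 | 1.71 | 2.11 |
| 0.1 | 1.20 | 1.80 | 2.22 |
| 0.11 | 1.32 | 1.98 | 2.44 |

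At 12 GBq every value passes. At 13.2 GBq the largest is 0.11 × 13.2 = 1.45 Gy, which also passes. Coefficients that pass the look but exceed the limit at 22.2 GBq run from 0.068 to 0.125 at 12 GBq, and from 0.068 to 0.083 at 18 GBq. Waiting for cycle 3 therefore removes most of the gap but not all of it: 0.077 passes at 18 GBq (1.39 Gy) and exceeds at 22.2 GBq (1.71 Gy).

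**A scaled limit at 12 GBq.** To keep 22.2 GBq within 1.5 Gy, the limit at 12 GBq would be 1.5 × 12 / 22.2 = 0.81 Gy. Both reported means fail it (0.92 and 1.20 Gy).

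**Staggered enrolment.** Suppose the first two subjects have had 18 GBq when the third reaches 12 GBq, with no reductions. At 0.077 the doses are 1.39, 1.39 and 0.92 Gy, so none of three exceeds. At 0.1 they are 1.80, 1.80 and 1.20 Gy, so two of three exceed. The least informative case is all three at exactly two cycles.

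**Individual reductions.** Protocol 1.6, 6.2 and 11.4.6 allow a subject's later activity to be cut to stay within limits. At 0.1 Gy/GBq, a third cycle of (1.5 − 1.20) / 0.1 = 3.0 GBq holds the total at 1.5 Gy, against 1.80 Gy at full activity. Achieved dose can then understate the dose at planned activity.

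**Kidney.** The thresholds are 23 / 12 = 1.92, 23 / 18 = 1.28 and 23 / 22.2 = 1.04 Gy/GBq. The available text gives no human kidney coefficient to set against them.

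**The case against.** The best defence is that two cycles is a floor: a decision at the end of cycle 3 also satisfies it, and the conditions on peptide mass point to waiting for Cohorts 3 and 6, as Protocol 11.6 does. That is a sensible reading of intent. It does not remove the Synopsis wording, which calls for initiation at the earlier point once its conditions are met.

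Second, the coefficients come from studies at about 100 µg peptide, while Cohort 1 uses 300 µg, and Protocol 1.6 warns that marrow dosimetry depends on the method. The safety review committee will have seen Part A dosimetry at 300 µg from at least six completed subjects. This stands: those values are not in the documents, so how plausible the 0.068 to 0.125 range is for this trial is unknown.

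Third, subjects are protected without the change. The criterion also requires no safety signal, the board reviews each escalation, organ doses are reported before each next cycle, and treatment stops above the limits. This also stands, so a reader should not infer that subjects would be taken past the limits unchecked.

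Fourth, the board already receives radiation exposure data. Its charter and Appendix 3 are not available, so it cannot be said that nobody projects dose for the next cohort. It can be said that no rule in the available text does.

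A reader might also infer that the SAP changed the timing and failed to list this in its Section 5. The documents do not support that. SAP Table 9 and Figure 4 carry the titles of Protocol Table 12 and Figure 15, so SAP 3.2.19 probably restates Appendix 3. The demonstrated conflict is between the Synopsis on one side and Protocol 11.6 and DRB-F on the other.

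**Conclusion.** The point holds and should be fixed, with medium confidence. At its earliest permitted look, the marrow condition for opening Cohort 2 is close to uninformative: it needs 0.125 Gy/GBq against reported values of at most 0.11, while anything above 0.068 exceeds 1.5 Gy at 22.2 GBq. The look is also earlier than Protocol 11.6 and DRB-F provide for. For Protocol 11.6 this follows from the cohort order and the wait for Cohorts 3 and 6 to finish; in DRB-F it is explicit.

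It would go too far to say the condition can never detect an exceedance. The result assumes nominal activity, coefficients borrowed from other studies, and all three subjects at two cycles; with two subjects at 18 GBq it would detect a coefficient of 0.095 or 0.1. Nothing is shown for kidney. The practical reach is limited, because Cohort 2 is optional, outside the priority order, and may be delayed or dropped. What remains is the risk of opening a cohort that may not be able to deliver its planned activity, under conflicting decision times.

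**What to change.** 1. Change the Synopsis trigger for Cohort 2 to the end of Cohort 1 cycle 3, consistent with Protocol 11.6 and the timing column of DRB-F.

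2. Take only the timing from DRB-F. Its conditions, as written, start Cohort 2 when DLTs exceed 33% in Cohorts 1 and 5. That reads as inverted against Protocol 3.8, under which more than 33% stops the next cohort. Correct them to at most 33%.

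3. At the Cohort 2 decision, give the board each subject's observed Gy/GBq for marrow and kidney multiplied by 22.2 GBq, set against 1.5 and 23 Gy. Add the number of subjects whose activity was reduced or stopped for dosimetry. The decision stays with the board.

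The cost is small: one sentence in the Synopsis, a correction to one table row, and one derived column. SAP 3.1.3(c) already computes Gy/GBq per organ at each administration, and the SAP listings already separate subjects by whether activity was adapted. The downside is more frequent flags and possibly a later start for Cohort 2.
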